5.7.3. Additional Safety Assessments

5.7.3.1. Clinical Laboratory Tests

Clinical laboratory tests will be displayed for the participants included in the safety analysis set.

Descriptive statistics will be presented for selected chemistry, hematology, and urinalysis (pH and specific gravity) laboratory tests at scheduled time points.

Change from baseline over time through Week 52 will be summarized for selected chemistry, hematology, and urinalysis (pH, and specific gravity) tests and displayed by intervention group. A box plot of change from baseline over time through Week 52 will be provided for the following laboratory tests: hematology: hemoglobin, platelets, total WBC, absolute lymphocytes, and absolute neutrophils; chemistry: ALT, AST, Alkaline phosphatase and total bilirubin.

Applicable lab results are to be graded based on National Cancer Institute Common Terminology Criteria for Adverse Events (NCI-CTCAE) version 5.0. The laboratory tests not included in the NCI-CTCAE criteria will not be presented in the corresponding tables or listings.

Summary of maximum postbaseline NCI-CTCAE toxicity grade through Week 52 will be presented. Additionally, shift table from baseline laboratory value to the worst toxicity grade through Week 52 in chemistry and hematology tests with NCI-CTCAE will be summarized for the following lab parameters: hematology: hemoglobin, platelets, total WBC, absolute lymphocytes, and absolute neutrophils; chemistry: ALT, AST, Alkaline phosphatase and total bilirubin.

Proportion of participants with maximum postbaseline ALT and AST through Week 52 will be provided for the categories:

- >1 to ≤ 3 x ULN
- >3 to ≤ 5 x ULN
- >5 to ≤ 10 x ULN
- >10 to ≤ 20 x ULN
- >20 x ULN

Besides, proportion of participants with total bilirubin >2 x ULN and either AST or ALT ≥ 3 x ULN at the same timepoint will also be provided.

In addition, proportion of participants with maximum postbaseline alkaline phosphatase through Week 52 will be provided for the categories:

- ≤ 1 x ULN
- >1 to ≤ 1.5 x ULN
- >1.5 to ≤ 2.5 x ULN
- >2.5 to ≤ 5 x ULN
- >5 to ≤ 20 x ULN
- >20 x ULN

Above analysis will also be summarized through LTE period.

Listings of participants with any abnormal postbaseline laboratory values of NCI-CTCAE grade ≥ 2 or any abnormal postbaseline laboratory values of reference range will also be provided.

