	Crohn's disease program in a participant who received guselkumab 1200 mg intravenous (IV) at Weeks 0, 4, and 8, and 200 mg subcutaneous (SC) at Week 12. Based on the hepatocellular pattern of injury, temporal relationship of the event to guselkumab exposure, and the exclusion of alternative etiologies, this event may represent druginduced liver injury possibly related to guselkumab. Alanine aminotransferase (ALT)/ aspartate aminotransferase AST abnormailities are a known risk for guselkumab, and that in the psoriatic arthritis studies, patients receiving guselkumab every 4 weeks (Q4W) were more likely to experience transaminase elevations than those receiving it every 8 weeks (Q8W).	accordance with regulatory guidance (FDA 2009). In addition, the induction doses evaluated in this clinical program will not exceed 400 mg IV. • Participants with marked liver enzyme elevations or symptoms or signs of liver dysfunction (eg, jaundice), should undergo a thorough investigation for possible causes of liver injury. A participant must have their study intervention discontinued if the participant has severe liver test abnormalities that are not transient and are not explained by other etiologies (Section 7.1 and Section 10.6).
Immunosuppression	It is unknown if guselkumab in combination with other immunosuppressives increases the risk of diseases associated with immunosuppression, such as infections or malignancy.	• In order to minimize the theoretical increased risk of infection or malignancy with the combination of guselkumab with immunosuppressive therapy, the baseline dose of oral corticosteroids on study entry is limited ≤10 mg of prednisolone or equivalent per day which must be at a stable dose ≥4 weeks prior to first dose of study intervention. Furthermore, participants receiving investigational or approved immunomodulatory agents like IL-23 inhibitor therapy, IL-12/23 inhibitors, or IL-17 inhibitors, failed for efficacy in SSc or within 12 weeks or 5 half-lives

CONFIDENTIAL – FOIA Exemptions Apply in U.S.

27

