6.10. Appendix 10 Laboratory Toxicity Grading

The grading scale use for lab assessments is based on ‘Common Terminology Criteria for Adverse Events (CTCAE) v5.0’.

If a laboratory value falls within the grading as specified below but also within the local laboratory normal limits, the value is considered to be normal and will be reset to grade 0.

Prebaseline measurements will use the same grading ranges as applied to baseline measurements. In case a test has two sets of ranges – one for baseline normal and one for baseline abnormal, the one for baseline normal will be applied for all measurements taken prebaseline and on baseline.

Text in gray italic in the table is present in the grading scale, but is not applied by Janssen when grading lab data.

CTCAE Term	Grade 1	Grade 2	Grade 3	Grade 4	Janssen implementation notes
Blood and lymphatic system disorders					
Anemia	Hemoglobin (Hgb) <LLN - 10.0 g/dL; <LLN - 6.2 mmol/L; <LLN - 100 g/L	Hemoglobin (Hgb) <10.0 - 8.0 g/dL; <6.2 - 4.9 mmol/L; <100 - 80g/L	Hemoglobin (Hgb) <8.0 g/dL; <4.9 mmol/L; <80 g/L; transfusion indicated	Life-threatening consequences; urgent intervention indicated	Clinical signs and symptoms are not taken into consideration for grading.
Leukocytosis	-	-	>100,000/mm ³ ; >100 x 10 ⁹ /L	Clinical manifestations of leucostasis; urgent intervention indicated	Clinical signs and symptoms are not taken into consideration for grading; Added ranges in SI unit (x 10 ⁹ /L)
Investigations					
Activated partial thromboplastin time prolonged	>ULN - 1.5 x ULN	>1.5 - 2.5 x ULN	>2.5 x ULN; bleeding	-	Clinical signs and symptoms are not taken into consideration for grading.
Alanine aminotransferase increased	>ULN - 3.0 x ULN if baseline was normal; 1.5 - 3.0 x baseline if baseline was abnormal	>3.0 - 5.0 x ULN if baseline was normal; >3.0 - 5.0 x baseline if baseline was abnormal	>5.0 - 20.0 x ULN if baseline was normal; >5.0 - 20.0 x baseline if baseline was abnormal	>20.0 x ULN if baseline was normal; >20.0 x baseline if baseline was abnormal	Ranges defined for “abnormal baseline” are applied only if baseline > ULN. If baseline < LLN, then ranges for “normal baseline” are applied.

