Alkaline phosphatase increased	>ULN - 2.5 x ULN if baseline was normal; 2.0 - 2.5 x baseline if baseline was abnormal	>2.5 - 5.0 x ULN if baseline was normal; >2.5 - 5.0 x baseline if baseline was abnormal	>5.0 - 20.0 x ULN if baseline was normal; >5.0 - 20.0 x baseline if baseline was abnormal	>20.0 x ULN if baseline was normal; >20.0 x baseline if baseline was abnormal	Ranges defined for “abnormal baseline” are applied only if baseline > ULN. If baseline < LLN, then ranges for “normal baseline” are applied.
Aspartate aminotransferase increased	>ULN - 3.0 x ULN if baseline was normal; 1.5 - 3.0 x baseline if baseline was abnormal	>3.0 - 5.0 x ULN if baseline was normal; >3.0 - 5.0 x baseline if baseline was abnormal	>5.0 - 20.0 x ULN if baseline was normal; >5.0 - 20.0 x baseline if baseline was abnormal	>20.0 x ULN if baseline was normal; >20.0 x baseline if baseline was abnormal	Ranges defined for “abnormal baseline” are applied only if baseline > ULN. If baseline < LLN, then ranges for

CTCAE Term	Grade 1	Grade 2	Grade 3	Grade 4	Janssen implementation notes
					“normal baseline” are applied.
Blood bilirubin increased	>ULN - 1.5 x ULN if baseline was normal; > 1.0 - 1.5 x baseline if baseline was abnormal	>1.5 - 3.0 x ULN if baseline was normal; >1.5 - 3.0 x baseline if baseline was abnormal	>3.0 - 10.0 x ULN if baseline was normal; >3.0 - 10.0 x baseline if baseline was abnormal	>10.0 x ULN if baseline was normal; >10.0 x baseline if baseline was abnormal	Ranges defined for “abnormal baseline” are applied only if baseline > ULN. If baseline < LLN, then ranges for “normal baseline” are applied.
CD4 lymphocytes decreased	<LLN - 500/mm ³ ; <LLN - 0.5 x 10 ⁹ /L	<500 - 200/mm ³ ; <0.5 - 0.2 x 10 ⁹ /L	<200 - 50/mm ³ ; <0.2 x 0.05 - 10 ⁹ /L	<50/mm ³ ; <0.05 x 10 ⁹ /L	
Cholesterol high	>ULN - 300 mg/dL; >ULN - 7.75 mmol/L	>300 - 400 mg/dL; >7.75 - 10.34 mmol/L	>400 - 500 mg/dL; >10.34 - 12.92 mmol/L	>500 mg/dL; >12.92 mmol/L	
CPK increased	>ULN - 2.5 x ULN	>2.5 x ULN - 5 x ULN	>5 x ULN - 10 x ULN	>10 x ULN	
Creatinine increased	Creatine Kinase >ULN - 1.5 x ULN	Creatine Kinase >1.5 - 3.0 x baseline; >1.5 - 3.0 x ULN	Creatine Kinase >3.0 x baseline; >3.0 - 6.0 x ULN	Creatine Kinase >6.0 x ULN	

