Hypomagnesemia	Magnesium <LLN - 1.2 mg/dL; <LLN - 0.5 mmol/L	Magnesium <1.2 - 0.9 mg/dL; <0.5 - 0.4 mmol/L	Magnesium <0.9 - 0.7 mg/dL; <0.4 - 0.3 mmol/L	Magnesium <0.7 mg/dL; <0.3 mmol/L; life-threatening consequences	Clinical signs and symptoms are not taken into consideration for grading.
Hyponatremia	Sodium <LLN – 130 mmol/L	Sodium 125-129 mmol/L and asymptomatic	Sodium 125-129 mmol/L symptomatic; 120-124 mmol/L regardless of symptoms Sodium <130-120 mmol/L	Sodium <120 mmol/L; life-threatening consequences	Clinical signs and symptoms are not taken into consideration for grading. Worst case (“<130-120 mmol/L” for grade 3 added by Janssen) is applied across grade 2/3 ranges: 120-129 mol/L

CTCAE Term	Grade 1	Grade 2	Grade 3	Grade 4	Janssen implementation notes
					assigned to grade 3, grade 2 not used.
Renal and urinary disorders					
Proteinuria	1+ proteinuria; urinary protein \geq ULN - <1.0 g/24 hrs; urinary protein \geq ULN - <1000 mg/day	Adult: 2+ and 3+ proteinuria; urinary protein 1.0 - <3.5 g/24 hrs; urinary protein 1000 - <3500 mg/day Pediatric: Urine P/C (Protein/Creatinine) ratio 0.5 - 1.9; Urine P/C (Protein/Creatinine) 56.5 - <214.7 g/mol	Adult: 4+ proteinuria; urinary protein $\geq=3.5$ g/24 hrs; urinary protein $\geq=3500$ mg/day; Pediatric: Urine P/C (Protein/Creatinine) ratio >1.9 ; Urine P/C (Protein/Creatinine) >214.7 g/mol	-	In case both 24-h urine collection and dipstick are collected, then worst case is taken, as opposed to having 24-h urine collection take precedence over dipstick. Added ranges in SI unit for urinary protein (mg/day) and for urine P/C (g/mol). Pediatric grading is applied to age range [0-18]. Adult grading is applied for ages [>18].

* Grade 0 is assigned to a lab assessment when the lab test is described in the table, but the lab value is not assigned a grade 1 or higher.

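### In the liver-test shift tables, baseline is graded against the ULN but later values against the participant's own raised baseline, so a stable abnormal value, or a moderate rise in ALT, AST or ALP, can appear as a move to Grade 0

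*SAP*

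**What the plan says.** SAP 5.7.3.1 grades laboratory results by NCI-CTCAE version 5.0. Besides a summary of the maximum post-baseline grade, it plans a "shift table from baseline laboratory value to the worst toxicity grade through Week 52 in chemistry and hematology tests with NCI-CTCAE". The chemistry tests in that table are ALT, AST, ALP and total bilirubin, and the analysis is repeated through the LTE.

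SAP Appendix 10 gives each of these four tests two sets of ranges, one for a normal and one for an abnormal baseline. For grading the baseline itself, "the one for baseline normal will be applied for all measurements taken prebaseline and on baseline". After baseline, the abnormal-baseline ranges "are applied only if baseline > ULN".

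For ALT, Grade 1 is ">ULN - 3.0 x ULN if baseline was normal" but "1.5 - 3.0 x baseline if baseline was abnormal"; AST is the same. For ALP the abnormal-baseline Grade 1 is "2.0 - 2.5 x baseline if baseline was abnormal". For bilirubin it covers values above 1.0 and up to 1.5 times baseline. The footnote to the table says "Grade 0 is assigned to a lab assessment when the lab test is described in the table, but the lab value is not assigned" Grade 1 or above. A separate rule resets values inside the laboratory's normal limits to Grade 0. Nothing in the SAP puts the two axes of the shift table on a common scale.

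**The concern.** A shift table is read by comparing the column with the row, which only works if both use the same scale. Here a participant with a raised baseline is placed on the ULN scale at entry and on a baseline-multiple scale afterwards. Grade 0 in the column can then mean either that the value returned to normal or that it stayed above the ULN without reaching the first baseline multiple. The table does not separate the two.

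This matters because liver enzymes are a named risk of the drug. Protocol 2.3.1, citing experience in psoriatic arthritis, reports that "patients receiving guselkumab every 4 weeks (Q4W) were more likely to experience transaminase elevations than those receiving it every 8 weeks (Q8W", and this trial doses every 4 weeks. Inclusion criterion 12 admits ALT and AST up to 2 x ULN at screening and sets no limit for ALP or bilirubin, so baselines above the ULN are possible.

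**Working it through.** The plan states no figure on this point, so there is none to reproduce. The check applies the Appendix 10 rules to example values.

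Inputs (SAP Appendix 10), with b = baseline and all values in multiples of ULN:

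- ULN-based ranges. ALT/AST: Grade 1 >1 to 3, Grade 2 >3 to 5, Grade 3 >5 to 20. ALP: Grade 1 >1 to 2.5, Grade 2 >2.5 to 5, Grade 3 >5 to 20. Bilirubin: Grade 1 >1 to 1.5, Grade 2 >1.5 to 3.
- Post-baseline ranges when b > 1. Grade 1 covers 1.5b to 3.0b for ALT/AST, 2.0b to 2.5b for ALP, and above 1.0b up to 1.5b for bilirubin.
- A value that reaches no grade is Grade 0.

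In the table below, ratio = worst post-baseline value / b. The SAP column grades baseline on the ULN ranges and the later value on the b ranges. The last column grades both on the ULN ranges.

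| Test | Baseline to worst value (x ULN) | Ratio | SAP rule | ULN ranges on both axes |
|---|---|---|---|---|
| ALT/AST | 2.0 to 2.0 | 1.00 | 1 to 0 | 1 to 1 |
| ALT/AST | 2.0 to 2.98 | 1.49 | 1 to 0 | 1 to 1 |
| ALT/AST | 2.0 to 3.8 | 1.90 | 1 to 1 | 1 to 2 |
| ALT/AST | 2.0 to 5.5 | 2.75 | 1 to 1 | 1 to 3 |
| ALP | 1.5 to 2.9 | 1.93 | 1 to 0 | 1 to 2 |
| ALP | 2.0 to 3.98 | 1.99 | 1 to 0 | 1 to 2 |
| ALP | 3.0 to 5.97 | 1.99 | 2 to 0 | 2 to 3 |
| Bilirubin | 1.4 to 1.4 | 1.00 | 1 to 0 | 1 to 1 |
| Bilirubin | 1.8 to 1.8 | 1.00 | 2 to 0 | 2 to 2 |
| Bilirubin | 1.4 to 1.47 | 1.05 | 1 to 1 | 1 to 1 |
| Bilirubin | 1.4 to 1.96 | 1.40 | 1 to 1 | 1 to 2 |

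In general terms:

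- ALT/AST: a baseline above 1 and up to 2 x ULN is Grade 1. Any later value below 1.5b is Grade 0, up to just under 1.5 x 2 = 3 x ULN.
- ALP: a baseline above 1 and up to 2.5 x ULN is Grade 1. Any later value below 2b is Grade 0, up to just under 2 x 2.5 = 5 x ULN.
- Bilirubin: any value above baseline is at least Grade 1, so Grade 0 requires that no post-baseline value exceeds baseline.

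The table takes the worst grade over 13 post-baseline visits (Weeks 4 to 52), so visit-to-visit variation affects how often this shows. An illustrative simulation took participants with stable levels who start above the ULN. It assumed mean levels of 1.7 x ULN for ALT/AST and ALP and 1.4 x ULN for bilirubin, with a within-person CV of 10%, 20% or 30%. None of these figures is in the documents. The chance that the worst post-baseline grade is 0 despite a value above the ULN was:

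- ALT/AST: 98%, 55%, 26%
- ALP: 100%, 95%, 77%
- Bilirubin: 7%, 8%, 8% (close to 1/14 = 7.1%, the chance that baseline is the largest of 14 exchangeable values)

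The documents do not give the number of participants who start above the ULN. If it were 5% to 20% of 56 on a given test, that would be 0.05 x 56 = 2.8 to 0.20 x 56 = 11.2, or about 3 to 11 people over both arms. This counts abnormal baselines, not misread cells.

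**The case against.** The rule is open and deliberate. The SAP commits to CTCAE version 5.0 and states which ranges apply when. A baseline cannot be graded as a multiple of itself, so some convention was needed. This stands: the grading ranges are not in dispute, only the use of two of them on the two axes of one table.

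SAP 5.7.3.1 speaks of the baseline laboratory value, not the baseline grade, so the row layout is not fixed. This also stands. Graded rows are plausible because Appendix 10 says how to grade a baseline. With normal/high rows the cell would read high to Grade 0, which still does not show whether the value normalised.

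Other outputs show the values. SAP 5.7.3.1 also plans ULN-multiple tables for ALT, AST and ALP, change-from-baseline summaries, and box plots for all four tests. It adds a combined bilirubin and transaminase criterion and a listing of post-baseline values outside the reference range. An ALT of 5.5 x ULN would appear in the >5 to 10 x ULN category and in the listing. These outputs limit the harm considerably. None of them is a shift display, and total bilirubin alone has no ULN-category table.

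A reader might infer three stronger things that the documents do not support:

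- That a rising bilirubin can look like an improvement. It cannot, because any rise is at least Grade 1.
- That liver monitoring is weakened. The stopping criteria (Protocol 7.1 and Appendix 6) and the Hy's law reporting rule (Protocol 8.3.1) are ULN-based and do not use these grades.
- That many participants will be affected. The screening limit permits ALT and AST above the ULN but does not say how often this will occur.

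**Conclusion.** The point holds as a defect in a descriptive safety display. Following the SAP exactly, a participant with ALT or AST above the ULN at baseline is shown at Grade 0 if the value stays stable or rises to less than 1.5 times baseline. For ALP the limit is 2.0 times baseline, and the starting grade can be 1 or 2. For bilirubin, only a value that never exceeds baseline goes to Grade 0, but a rise can be understated by a grade. The Grade 1 to 0 reading assumes that the rows are baseline grades.

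The mechanism follows from Appendix 10 and needs no outside assumption. How often it occurs depends on the number of raised baselines and on within-person variation, neither of which the documents give. Efficacy analyses, data collection and liver-safety rules are not touched. It is worth correcting because it follows from a stated rule, concerns a named risk of the drug, and can be put right in one sentence.

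**What to change.** Add to SAP 5.7.3.1 and Appendix 10: for the ALT, AST, ALP and total bilirubin shift tables, baseline and post-baseline values are both graded on the ULN-based (baseline normal) ranges. Keep the CTCAE v5.0 baseline-multiple grade for the maximum-grade summary. Put a footnote on both tables that names the reference used and explains the difference. Stating whether the shift-table rows are baseline grades or normal/high categories would settle the layout at the same time.

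The cost is one SAP sentence, one programming rule and two footnotes. The small downside is that one value can carry different grades in the two tables: an ALT going from 2.0 to 5.5 x ULN would be Grade 3 in the shift table and Grade 1 in the maximum-grade summary. The footnotes are there to explain this. A lighter alternative is to keep the present grading, footnote the two references, and show participants with a baseline above the ULN separately. That warns the reader but leaves the two axes on different scales.

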- h. Screening should occur within 6 weeks prior to W0 visit. The study visit week are indicated and calculated based on the day of randomization/first administration of the study intervention (W0 visit). Visit window should be ±7 days for each visit (Visit window for W0 visit should be -7 days).
- i. Pulmonary function tests include forced vital capacity (FVC) and diffusing capacity of the lung for carbon monoxide (DLCO). If decline in % predicted FVC ≥ 15 % (relative) is seen, another FVC test needs to be performed within a month.
- j. To be measured at a central laboratory
- k. Participants with potential active tuberculosis need to pause the study intervention administration until the tuberculosis assessment is completed.
- 1. For participants with stent, HRCT cannot be centrally read.
- m. For screening, information on ACR CRISS step 1 will be collected as SSc Condition of Interest.
- n. For participants who will NOT enter LTE, refer to Week 52 in Table 1. For participants who will enter LTE, refer to Week 52 and the subsequent visits in Table 2.
- o. Only participants who will NOT enter LTE should perform the safety follow up visit at Week 60.
- p. ICF for participation of LTE should be obtained at the latest at Week 52.

Table 2: Long-Term Extension for Eligible Participants Who Have Completed the Main Study (LTE)

Period		Long-term extension (LTE)									Safety Follow-up (LTE- EOS)	Early Termination Visit (LTE- ET)				
LTE Week ^a	52	56	60	64	68	72	76	80	84	88	92	96	100	104	112	
Study Procedure																
Administrative																
ICF for participation of LTE ^b	(X)															
Study Intervention Administration																
Administer study intervention ^c	X	X	X	X	X	X	X	X	X	X	X	X	X			
Training for self-administration ^d		X	X	X				**********				···>				
(Optional)																
At-home administration ^e (Optional)									X		X		X			
Efficacy Assessmentsf																
mRSS ^g	X	X	X	X	X	X	X	X		X		X		X		X
Physician's global assessment	X			X			X			X				X		X
Digital ulcer assessment	X			X			X			X				X		X
Patient's global assessment	X			X			X			X				X		X
HAQ-DI	X			X			X			X				X		X
FSSG	X			X			X			X				X		X
Nailfold capillaroscopy	X															
Lung HRCT (centrally read)h	X						X							X		
Pulmonary function tests ⁱ	X			X			X							X		X
ACR CRISS	X			X			X							X		X
Safety Assessments ^j																
Physical examination	X	X	X	X	X	X	X	X		X		X		X	X	X
Weight	X			X			X							X		X
Vital signs	X	X	X	X	X	X	X	X		X		X		X	X	X

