Serious adverse events, including those spontaneously reported to the investigator within 12 weeks after the last dose of study intervention, must be reported. The sponsor will evaluate any safety information that is spontaneously reported by an investigator beyond the time frame specified in the protocol. Possible Hy's law case (AST or ALT \geq 3 x ULN together with total bilirubin \geq 2 x ULN or INR > 1.5) is considered an important medical event and must be reported to the sponsor in an expedited manner using the Serious Adverse Event Form, even before all other possible causes of liver injury have been excluded. (INR criterion is not applicable to participants receiving anticoagulants.)

Information regarding SAEs will be transmitted to the sponsor using the Serious Adverse Event Form, which must be completed and signed by a physician from the study site, and transmitted to the sponsor within 24 hours. The initial and follow-up reports of an SAE should be made by facsimile (fax). Telephone reporting should be the exception and the reporter should be asked to complete the appropriate form(s) first.

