≥2xULN or INR >1.5: • Repeat liver chemistry tests (include ALT, aspartate transaminase [AST], alkaline phosphatase, total bilirubin, and INR) and		Record the appearance or worsening of clinical symptoms of liver injury, or hypersensitivity, on the liver event/expedited reporting form		
 perform liver event follow-up assessments within 24 hours Monitor participant twice weekly until liver chemistry test abnormalities resolve, stabilize, or return to baseline 		Record use of concomitant medications (including acetaminophen, herbal remedies, and other over-the-counter medications) on the concomitant medications CRF		
 A hepatology consultation is recommended If ALT or AST≥3xULN AND total bilirubin <2xULN and INR ≤1.5: 				

CONFIDENTIAL – FOIA Exemptions Apply in U.S.

- Repeat liver chemistry tests (include ALT, AST, alkaline phosphatase, total bilirubin and INR) and perform liver chemistry follow-up assessments within 24 to 72 hours
- Monitor participants weekly until liver chemistry abnormalities resolve, stabilize, or return to baseline
- **Do not restart/rechallenge** participant with study intervention unless allowed per protocol and sponsor approval is granted

If ALT or AST≥3xULN AND total bilirubin ≥2xULN or INR >1.5 obtain the following in addition to the assessments listed above:

- Anti-nuclear antibody, anti-smooth muscle antibody, Type 1 anti-liver kidney microsomal antibodies, and quantitative total immunoglobulin G (IgG) or gamma globulins
- Serum acetaminophen adduct assay, when available, to assess potential acetaminophen contribution to liver injury in participants with definite or likely acetaminophen use in the preceding week
- Liver imaging (ultrasound, magnetic resonance, or computerized tomography) to evaluate liver disease; complete liver imaging form
- Liver biopsy may be considered and discussed with local specialist if available, for instance:

In participants when serology raises the possibility of autoimmune hepatitis (AIH)

In participants when suspected drug-induced liver injury (DILI) progresses or fails to resolve on withdrawal of study intervention

In participants with acute or chronic atypical presentation

- If liver biopsy conducted complete liver biopsy form

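### The SAP's only combined liver laboratory count is narrower than the protocol's possible Hy's law definition, and Week 60 chemistry from participants who skip the LTE has no clear place in the liver maxima

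*SAP*

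**What the plan says.** **The combined count.** SAP 5.7.3.1 (Clinical Laboratory Tests) says that the proportion of participants with total bilirubin above 2×ULN and AST or ALT at or above 3×ULN "at the same timepoint will also be provided". It has no INR component and no week limit of its own.

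**The protocol definition.** Protocol 8.3.1 calls a case possible Hy's law when AST or ALT is at least 3×ULN together with total bilirubin at least 2×ULN or INR above 1.5. INR is not used for participants on anticoagulants. Such a case "is considered an important medical event and must be reported to the sponsor in an expedited manner using the Serious Adverse Event Form".

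**Repeat testing.** Protocol Appendix 6 (10.6) asks for repeat liver tests, including INR, within 24 hours or within 24 to 72 hours depending on the pattern, with twice-weekly or weekly monitoring afterwards. INR is not in the routine laboratory list in protocol Appendix 2 (10.2).

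**Time window of the tables.** SAP 5.7.3.1 states: "Proportion of participants with maximum postbaseline ALT and AST through Week 52 will be provided for the categories". The alkaline phosphatase maxima, maximum toxicity grade and worst-grade shift tables carry the same Week 52 limit. After the liver items the section adds: "Above analysis will also be summarized through LTE period".

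**Week 60.** The Schedule of Activities (protocol 1.3, Table 1) has chemistry at the Week 60 follow-up, and its footnote o says: "Only participants who will NOT enter LTE should perform the safety follow up visit at Week 60".

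**The concern.** The count is the only place where the SAP combines transaminases and bilirubin into a proportion by arm. A reader will naturally take it as the possible Hy's law row. If its definition is narrower than the protocol's, the row can read zero for an arm in which the site has reported a possible Hy's law case.

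Liver injury is a listed risk in protocol 2.3.1. That section reports one possible drug-induced case in the Crohn's disease program and says transaminase elevations were more likely with Q4W than with Q8W dosing in the psoriatic arthritis studies. Maintenance here is Q4W. The reported case followed 1200 mg IV, and protocol 4.3 puts exposure at 400 mg IV at about one third of that, so this context should not be overplayed. In an arm of 28, though, a single case is the whole signal, and the row should be able to show it.

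The Week 60 issue is similar. Values taken 12 weeks after the last dose (Week 48 + 12 = Week 60) are post-treatment safety data, and the main-study maxima do not use them.

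**Working it through.** The plan states no figure for this tabulation, so there is nothing to reproduce. The check applies the two written rules to the same hypothetical results.

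**Rules**

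- Protocol 8.3.1: (ALT or AST ≥3×ULN) together with (bilirubin ≥2×ULN or INR >1.5). No time window is given.
- SAP 5.7.3.1: (ALT or AST ≥3×ULN) and (bilirubin >2×ULN), same timepoint.

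**Hypothetical patterns** (ALT and bilirubin in multiples of ULN; participant not on anticoagulants)

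| Pattern | Protocol 8.3.1 | SAP count |
|---|---|---|
| A. ALT 4, bilirubin 2.5, same draw | Yes | Yes |
| B. ALT 4, bilirubin 1.2, INR 1.8, same draw | Yes | No |
| C. ALT 4, bilirubin exactly 2.0, same draw | Yes | No |
| D. ALT 4 with bilirubin 1.0, then ALT 2.0 with bilirubin 2.5 four weeks later | Depends on the reading of together | No |
| E. ALT 4, bilirubin 2.5, same draw at Week 76 | Yes | Yes, through the LTE summary |

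B and C are definite mismatches. D is an ambiguity. E shows that LTE cases are covered.

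**Size.** One missed case in an arm of 28 changes 1/28 = 3.6% to 0/28 = 0% in this row.

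**Which draws count.** Scheduled visits are four weeks apart, while the Appendix 6 repeats come within days and then weekly or twice weekly. SAP 5.1.4 uses nominal visits for by-visit analyses, and 5.7.3.1 does not mention unscheduled samples. By contrast, SAP 5.7.3.3 expressly includes unscheduled data in its ECG listings. Because INR is requested only in the repeat tests, adding an INR condition while restricting the count to scheduled visits would achieve almost nothing. The two changes have to be made together.

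**Week 60.**

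1. A participant who completes Week 52 and does not enter the LTE has chemistry at Week 60.
2. The ALT, AST and alkaline phosphatase maxima and the worst-grade tables run through Week 52, so that value is outside them.
3. The sentence extending the analysis to the LTE names no analysis set. The LTE safety set in SAP Section 4 requires at least one dose during the LTE, so on that set the participant is absent.
4. The combined count has no week limit, so whether it includes Week 60 is left open.

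The number of non-entrants is not stated, so the volume of data affected cannot be calculated.

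**The case against.** **Other outputs show the case.** This largely stands. A case on the SAE form enters the SAE table and listing (SAP 5.7.2). It may fall in the drug-induced liver injury category (SAP Appendix 8) if its coded term is in the search. SAP Appendix 10 grades INR above 1.5 as grade 2 or higher, and the listing of grade 2 or higher or out-of-range values has no week limit. So an INR held in the laboratory database, or an abnormal Week 60 value, would be listed. A reader might infer that possible Hy's law cases vanish from the report; the documents do not support that. What remains is that none of these outputs is a count by arm labelled as possible Hy's law, and the Appendix 8 search works on coded terms, not laboratory values. The SAE route also rests on protocol wording that differs between sections: 8.3.1 sends every possible case to the SAE form, while the Appendix 6 footnote makes SAE reporting depend on SAE criteria and adds a direct-bilirubin condition. Those passages must be reconciled.

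**Protocol 8.3.1 is a reporting rule, not a tabulation rule.** True, so the SAP breaks no explicit instruction. But the mismatch is unexplained.

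**The liver tables do not stop at Week 52.** Correct for LTE entrants. The limits, read alone, suggest that later data are dropped, but the LTE sentence answers that. Only Week 60 in non-entrants remains unclear.

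**A same-timepoint rule is compatible with the protocol.** Also correct. A reader might infer that bilirubin rising after ALT has fallen is a protocol case that the SAP misses. The protocol sets no window, and Appendix 6 does not say that its repeats serve this purpose. Pattern D is therefore no contradiction.

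**Conclusion.** The point holds as a minor misalignment. SAP 5.7.3.1's combined count misses two kinds of case that meet protocol 8.3.1: those qualifying on INR alone and those with bilirubin exactly 2×ULN. It also leaves the use of repeat tests unstated. Its effect is confined to one row, where a single such case would show as 0% instead of 3.6% of a 28-participant arm. Separately, Week 60 chemistry from non-entrants is outside the main-study liver maxima and worst-grade tables and not clearly inside the LTE summary.

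This assumes that same timepoint means one draw or one nominal visit and, for the percentage, that the planned 28 per arm are all in the safety set. How often an INR-only or exactly-2×ULN case would arise cannot be judged from the documents.

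**What to change.** Change the SAP analysis only; clinical management is untouched.

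- **Definition.** Count participants with ALT or AST ≥3×ULN and either bilirubin ≥2×ULN or INR >1.5, with the anticoagulant exception, as in protocol 8.3.1. State how the count treats the direct-bilirubin condition once the sponsor has reconciled 8.3.1 with Appendix 6.
- **Data used.** State that scheduled and unscheduled results both count, and define same timepoint (for example, same collection date). A supplementary count over a fixed following window is optional.
- **Window.** Run the main-study liver maxima and worst-grade tables through Week 52 for LTE entrants and through the Week 60 follow-up for non-entrants. State the same window for the combined count. Keep the existing LTE summary.

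The cost is a few lines of SAP text and minor programming. Week 60 chemistry is already scheduled. The INR component works only if follow-up INR results reach the analysis database, which the documents do not confirm; the sponsor should check this before finalizing the SAP.
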